5.2 Concomitant Medications

5.2.1 Disallowed Medications

Study participants should not receive immunosuppressant agents or chemotherapy and should preferably not be given high doses of steroids (defined as >40 mg or 0.5 mg/kg prednisone (or steroid with equivalent activity)/day for \geq 2 weeks (see Appendix F – Section 15.6).

NOTE: Adrenal replacement therapy (corticosteroids) is permitted in patients with septic shock at the discretion of the Investigator balancing the potential benefits and risks in this situation. The optimal treatment regimen in this setting is not resolved. Investigators are referred to current Surviving Sepsis Campaign guidelines (www.survivingsepsis.org) as a reasonable source of guidance for steroid replacement therapy in septic shock patients.

5.2.2 Allowed Medications

5.2.2.1 Antimicrobial agents

All patients will receive one or more antimicrobial drugs used as SoC to treat the primary or subsequent infections. Antimicrobial agents include antibacterial, anti-fungal, anti-viral and anti-parasitic drugs. Topically applied antimicrobial agents should be included. Any other medications whether drugs or biologics used to treat the patient should be identified as non-antimicrobial medications.

Each antimicrobial agent will be identified by its generic or trade name and reported in the eCRF. Information should include the dose, dosing frequency, route of administration, duration (start and stop times and dates), and reason for administration (to treat primary or secondary infection or for surgical prophylaxis).

5.2.2.2 Non-antimicrobial medications

All non-antimicrobial (ancillary) drugs administered from the time of patient screening until end of study will be recorded in the eCRF. Information to be collected should include generic or trade name, route of administration, duration (start and stop dates) and reason for administration. A list of medications that are not required to be captured in the ancillary medication eCRF is provided in the Study Procedure Manual.

5.3 Study Medication Compliance

Compliance will be monitored by recording the total volume of each investigational agent actually delivered to each study patient.

5.4 **Precautions and Overdose**

5.4.1 Study Drug - AB103

5.4.1.1 Precautions

Currently available safety information does not require any special precautions to be exercised during treatment with AB103. Analysis of safety data collected in AB103 Phase 1 and 2 studies, did not reveal AEs that were determined as related to AB103 (including

possibly, probably and definitely related to study drug). In animal toxicology studies no target organs were identified.

5.4.2 Placebo Comparator

No known or expected adverse reactions are associated with pyrogen-free, preservativefree, physiologic saline.

5.4.2.1 Precautions

None for placebo comparator.

6. STUDY PROCEDURES

6.1 Informed Consent

The ICF must be in compliance with ICH GCP Guidelines, and in accordance with the Federal Regulations as detailed in 21 CFR §50.25 and the Declaration of Helsinki.

Prior to entering the study, the Investigator/designee must explain the nature of the study to each patient or legal representative, its purpose, expected duration, alternative forms of therapy available and the benefits and risks of study participation. After this explanation and before entering the study, the patient or legal representative must read and understand the ICF and voluntarily sign a consent form in the presence of the Investigator/designee.

The patient will be given a copy of the signed/dated ICF.

6.2 Clinical and Laboratory Procedures

6.2.1 Start of Drug Administration Clock

The IV drug administration clock of maximal 6 hours starts once a clinical diagnosis has been made in the study site and a documented decision is made to take the patient into the operating room for a surgical exploration and debridement and confirmation of the diagnosis. The exact time of decision to operate should be recorded.

6.2.2 Inclusion/Exclusion Criteria

The inclusion and exclusion criteria are specified in Sections 3.1 and 3.2. These criteria determine patient eligibility for recruitment. All patients must be evaluated for the presence of all inclusion criteria and the absence of all exclusion criteria before they are eligible to receive study drug.

6.2.3 Medical and Surgical History

A complete medical history identifying clinically relevant past medical and surgical conditions and active medical or surgical conditions will be reported on the Medical History eCRF. All chronic medications will be identified and characterized by trade or generic name, route of administration as well as reason for use.

Baseline signs and symptoms should be captured on the Adverse Event eCRF with attempts to capture dates and times that would identify them as pre-treatment emergent events.

Details of the NSTI will be recorded on the eCRF and include: "clinical diagnosis" (as a specific subset of NSTI) at the time of enrollment; location of primary infection; date of onset of symptoms, identified predisposing factors (trauma, surgery, IV drug use, and co-morbidities such as diabetes or vascular insufficiency; prior surgical procedures related to the etiology of NSTI; prior surgical procedures for the treatment of the primary infection site; antimicrobial use from the date of onset of current illness (may predate diagnosis of NSTI); description of the NSTI lesion; date and time of surgical intervention for NSTI and surface area of NSTI debridement (when available).

6.2.4 Physical Examinations

Physical exam will include both the primary site of the NSTI and a clinically appropriate examination of vital organ systems. These should include cardiovascular, respiratory, abdomen, extremities, and neurologic body systems.

6.2.4.1 Interim physical examinations (symptom-driven)

Interim physical exam will be targeted to include clinically appropriate examination of specific organ systems based on patient related signs and symptoms.

6.2.5 Concomitant Medication

All concomitant medications antimicrobial & non-antimicrobial (with the exception of over the counter medications, vitamins, laxatives, intravenous fluid and electrolyte replacement, parenteral nutrition, topical medications and other selected medications as described in the Study Procedure Manual) will be entered into the eCRF and identified by their generic or trade name. Information about antimicrobial medications should include the dose, dosing frequency, route of administration, duration (start and stop times and dates), and reason for administration to be collected about non-antimicrobial medications should include generic or trade name, route of administration, duration (start and stop times and dates) and reason for administration to be collected about non-antimicrobial medications should include generic or trade name, route of administration, duration (start and stop dates) and reason for administration.

Timing and adequacy of antibiotic therapy (based on institutional guidelines, baseline pathogens and antimicrobial sensitivity) will be reviewed by the Principle Investigator.

6.2.6 Primary Infection Site

The primary infection site will be described in detail. Any visible wound or drainage will be characterized as to amount, and cellular composition (purulent, sero-sanguineous, sanguineous, other). Tissue edema, focal pain and presence of subcutaneous crepitus, the presence of tissue discoloration, blisters, bullae or necrosis will be identified. The extent of progression of necrosis as well as the need for repeated surgical procedures will be documented by the Investigator.

6.2.6.1 Debridement

A debridement is defined as a surgical intervention, performed in the operating room to eliminate a substantial amount of necrotic tissue, based on the description by the surgeon in the operative note. Irrigation of the wound or dressing change in the operating room without tissue removal will not be considered a debridement. Also, minimal procedures to trim margins are not considered a true debridement, nor are bedside procedures, such as a dressing change or Vacuum Assisted Closure (VAC) change.

All operative procedure reports (following appropriate de-identification) will be collected up through Day 14 and any operative reports related to amputations will be collected through Day 28. An adjudication panel of 3 surgeons (investigators involved in the clinical trial) will evaluate the operative reports, in a blinded manner, to assign whether an operative procedure meets the debridement definition as noted above.

6.2.7 Vital Signs

Vital signs include heart rate, systolic and diastolic blood pressure, respiratory rate (spontaneous, assisted or controlled) and temperature. While these may be determined many times during the course of the patient's hospitalization, recording vital signs (first set of vitals on that day) in the eCRF will be based on once daily readings for specified time sequences according to time and events, Appendix A, Section 15.1.

6.2.8 Clinical Scores

Clinical scores/criteria components will be collected in the study. APACHE II, LRINEC and Anaya score criteria only at screening while mSOFA score throughout the study (see Appendix E, Section 15.5). APACHE II, LRINEC and Anaya criteria will be used to determine disease severity while mSOFA score will be used as a clinical endpoint. Individual parameters of the mSOFA score will be collected and will also be correlated to response. Clinical site personnel will calculate the mSOFA at screening to determine patient eligibility, otherwise all other clinical scores will be calculated retrospectively by the blinded statisticians. (See scores details in Appendix E, Section 15.5). Data will be recorded in the eCRF at specified time points according to time and events Section 15.1.

6.2.8.1 SOFA score definition

Screening mSOFA: includes measurements of 5 organ systems (cardiovascular, respiratory, renal, coagulation, CNS but not liver/hepatic component). Screening mSOFA score should be evaluated any time after arrival at the study site hospital, although no more than 6 hours prior to anticipated first debridement. Screening mSOFA score must be \geq 3, with any one organ component having a score of at least 2, to be considered eligible for enrollment. Sites are encouraged to re-evaluate mSOFA score as close to surgery as feasible for patients not meeting mSOFA \geq 3 inclusion criteria during initial screening.

mSOFA score: measurements of a 5 organ systems, including CNS. To be measured on Days 1, 2, 3, 7, 10 14, 21 and 29 and calculated retrospectively by the blinded statisticians. *mSOFA respiratory parameter*:

In case it is not possible to take arterial blood gases to determine the mSOFA respiratory parameter, SpO2/FiO2 ratio can be imputed for PaO2/FiO2 ratio.

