^q Tissue for microbiology will be taken at the 1st debridement (performed at visit 1), to be used for identification of pathogen(s), susceptibility to antimicrobial drugs and Gram stain. Obtain tissue for microbiological culture if debridement performed on Day 3 (Visit 4). If culture from debridement on Day 3 is positive, then repeat culture if subsequent debridement(s) performed.

^r Adverse events including SAEs will be collected from obtaining ICF through day 28; AEs that are not resolved should be followed-up until resolution or until determined as stable and due to known cause.

^s AEs of day 0 are baseline AEs (not TEAE) starting after obtaining ICF until study drug administration.

^t Assess lesion status (healing/progression/significant change in appearance) if accessible for visible assessment at time of debridement or routine dressing change

Visit	1	2	3	4	5	6	7	8	9	10
	Screening	Day 1	Day 2	Day 3	Day 7 ±1 day	Day 10 ±1 day	Day 14 ±1 days	Day 21 ±1 days	Day 29 +2 days	3 months ±5 days
Collect data on acute renal replacement therapy, plasma and/or platelet transfusion									•	
Evaluation of adequacy of antimicrobial treatment				Х						
Critical care and hospital stay parameters ^u										
mSOFA score ^v	Х	X ^w	Х	Х	Х	Х	Х	Х	Х	
APACHE II score ^x	X									
LRINEC and Anaya ^y scores	Х									
Survival										
Hospital readmissions ^z									Х	Х
Serum for immunogenicity ^{aa}	X						Х		Х	X

^u Hospital length of stay (days), ICU stay (days), ICU free days, Mechanical ventilation days/mechanical ventilation free days;

^v Screening mSOFA: To be calculated prospectively from time patient presents at the hospital (may include referring hospital) but within 6 hours prior to first debridement. Screening mSOFA may be reassessed up to actual time of surgery if initial mSOFA evaluation had score <3. To include measurements of 5 organ systems to achieve score of \geq 3, in any one or more organs, with any one organ having a score of at least 2: cardiovascular, respiratory, renal, coagulation and CNS (To include evaluation of oxygenation either directly by arterial blood gas test or by calculation of PaO₂ from SpO₂, in case it is not possible to obtain arterial blood to determine the SOFA respiratory parameter), ^w Subsequent mSOFA data collection (Days 1, 2, 3, 7, 10, 14, 21 and 29): taken once a day, in the morning (between 6AM until 12 noon) adjusted to the time of normal

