15.3 Appendix C - modified SOFA

Value	0	1	2	3	4
Respiratory PaO ₂ /FiO ₂ ¹	>400	≤400	≤300	≤200 with respiratory support	≤100 with respiratory support
Coagulation Platelets	>150	≤150	≤100	≤50	≤20
Cardiovascular ²	No hypo- tension	MAP <70	Dopa ≤5 PE <100	Dopa > 5 Epi ≤ 0.1 NE ≤ 0.1 PE 100- 300	Dopa>15 Epi>0.1 NE>0.1 PE>300 VP>0.01
Neuro GCS	15	13-14	10-12	6-9	<6
Serum Creatinine OR Urine Output	<1.2	1.2-1.9	2.0-3.4	3.5-4.9 <500cc/ day	≥5.0 <200cc/ day

1. For patients on supplemental oxygen via nasal cannula, nasopharyngeal catheter or mask and for converting SpO2 values to PaO2 use the attached oxygen conversion tables.

2. Doses of dopamine (Dopa), epinephrine (Epi), norepinephrine (NE) are in micrograms/kg/min; phenylephrine (PE) is micrograms/min; vasopressin (VP) is U/min. Vasopressors must have been administered for at least one hour.

Oxygen Conversion tables

Estimating Pa02 from a given Sp02

SpO2 (%)	PaO2 (mmHg)
80	44
81	45
82	46
83	47
84	49
85	50
86	52
87	53
88	55
89	57
90	60
91	62
92	65
93	69
94	73
95	79
96	86
97	96
98	112
99	145

Estimating Fi02

Method	O2 flow	Estimated FiO2 (%)
Nasal cannula	1	24
	2	27
	3	30
	4	33
	5	36
	6	40
Nasopharyngeal catheter	4	40
	5	50
	6	60
Face mask	5	40
	6-7	50
	7-8	60
Face mask with reservoir	6	60
	7	70
	8	80
	9	90
	10	95

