15.5 Appendix E - Clinical Scores

Table 7: Clinical Scores Parameters

Parameter	LRINEC	Anaya	mSOFA	APACHE II
Clinical				
Cardiovascular system (Mean Arterial Pressure)			+	+
Heart Rate		+		+
Nervous system (Glasgow Coma Score)			+	+
Oxygenation (Calculation)			+	+
			(PaO ₂ /FiO ₂)*	(Pao2 or A-a difference)
Respiratory rate				+
Temperature				+
		Т		(rectal)
Demographics				
Age		+		+
Chronic health evaluation				+
Laboratory				
Arterial pH				+
Coagulation Function (Platelets)			+	
C-Reactive Protein	+			
Renal system / Creatinine	+	+	+	+
Glucose	+			
Hemoglobin/Hematocrit	+	+		+
Sodium	+			+
Potassium				+
Total white cell count	+	+		+

*In case it is not possible to obtain arterial blood gases to determine the SOFA respiratory parameter, SpO2/FioO2 ratio can be imputed for PaO2/FiO2 ratio

Immunosuppressive Agent ^a	Upper limit dosage use	
1. Corticosteroid	> 40 mg/day of prednisone or its equivalent daily for $>$ 2 weeks.	
Equivalent Dose (mg)		
a) Prednisone	40 mg	
b) Hydrocortisone	160 mg	
c) Methylprednisolone	32 mg	
d) Dexamethasone	6 mg	
e) Cortisone	200 mg	
f) Betamethasone	4.8 mg	
2. Methotrexate (Rheumatrex, Trexall)	Excluded at any dose.	
3. Leflunomide (Arava)/Teriflunomide (Aubagio)	Acceptable if being used as monotherapy.	
4. Cyclophosphamide (Cytoxan)	Excluded at any dose.	
5. Cyclosporine A	Excluded at any dose.	
	Ophthalmic formulation (Restasis) is permitted	
6. FK506 (Tacrolimus)	Excluded at any dose	
	Topical formulation (Protopic) is permitted.	
7. Azathioprine	Excluded at any dose.	
8. Cancer Chemotherapy	Patients having received cancer chemotherapy in the previous 4 weeks are excluded.	

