SOFA – Sequential Organ Failure Assessment score

Can range from 0 -24

Respiratory system:

PaO ₂ / FiO ₂ (mmHg)	SOFA score
=>400	0
< 400	1
< 300	2
< 200 and mechanically ventilated	3
< 100 and mechanically ventilated	4

Nervous System:

Glasgow Coma Scale	SOFA score
15	0
13-14	1
10-12	2
6-9	3
< 6	4

Cardiovascular System

Mean Arterial Pressure (MAP) OR administration of vasopressors (mcg/Kg/minute)	SOFA score
$MAP \Rightarrow 70 \text{ mmHg}$	0
MAP < 70 mmHg	1
Dopamine <= 5 OR Dobutamine any dose	2
Dopamine > 5 <=15 OR epinephrine <=0.1 OR norepinephrine <= 0.1	3
Dopamine > 15 OR epinephrine > 0.1 OR norepinephrine > 0.1	4

MAP= (Systolic pressure + (2*Diastolic pressure))/3

Liver:

Bilirubin (mg/dl)	SOFA score
<1.2	0
1.2-1.9	1
2.0-5.9	2
6.0-11.9	3
>= 12.0	4

Coagulation:

Platelets x 10 ³ /mcl	SOFA score
=>150	0
< 150	1
< 100	2
< 50	3
< 20	4

Renal System:

Creatinine (mg/dl) (or urine output)	SOFA score
<1.2	0
1.2 - 1.9	1
2.0 - 3.4	2
3.5 - 4.9 (or < 500 ml/day)	3
>=5.0 (or < 200 ml/day)	4

Anaya score

Can range from 0 - 12

Variable on admission	Points
Heart Rate > 110 beats per minute	1
Temperature < 36.0 °C	1
Serum Creatinine > 1.5 mg/dl	1
Age > 50	3
White blood cells count > 40,000/mcl	3
Hematocrit > 50%	3

LRINEC – Laboratory Risk Indicator for Necrotizing Fasciitis

Can range from 0 - 13

	П
Variable, Units	Score
C-Reactive Protein mg/L	
< 150	0
>= 150	4
Total White Blood cells count per mm ³	
< 15	0
15 - 25	1
>25	2
Hemoglobin g/dL	
>13.5	0
11.0 – 13.5	1
< 11	2
Sodium mmol/L or meq/L	
>= 135	0
< 135	2
Creatinine µmol/L (mg/dL)	
<= 141 (1.595)	0
>141 (1.595)	2
Glucose mmol/L (mg/dL)	
<=10 (180.18)	0
>10 (180.18)	1

16 Appendix 6: Randomization Program: SAS call to R program

```
proc format;
value treatment fmt
  1 = 'Placebo'
  2 = 'Active'
run;
proc iml;
submit / R;
library(doParallel)
site hold <- seq(10, 49, by = 1)
strata hold <- c(1,2,3,4)
block 4 < -c(1,1,2,2)
block_6 <- c(1,1,1,2,2,2)
theseed = 42
set.seed(theseed)
site loop <- foreach (si = site hold, .combine=rbind) %do% {</pre>
  site num <- si
  strata loop <- foreach (s = strata hold, .combine=rbind) %do% {</pre>
    strata num <- s
    full block <- foreach (i =1:5, .combine=rbind) %do% {</pre>
      get random block <- rbinom(1, 1, 0.5)</pre>
      if (get random block == 1) {
        block <- sample(block 6, 6, replace = FALSE)
      if (get random block == 0) {
        block <- sample(block 4, 4, replace = FALSE)</pre>
      full block <- as.matrix(block)</pre>

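### The protocol gives two different rules for scoring the mSOFA lung component from pulse oximetry, they can differ by up to 2 points, and the SAP does not say which applies

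*Protocol*

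**What the plan says.** **Direct ratio.** Protocol 6.2.8.1 states that, without blood gases, the "SpO2/FiO2 ratio can be imputed for PaO2/FiO2 ratio". The synopsis has the same sentence, and the Appendix E footnote says the "SpO2/FioO2 ratio can be imputed for PaO2/FiO2 ratio". None of the three refers to a conversion table.

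**Conversion.** Footnote 1 to the mSOFA table in Protocol Appendix C says "for converting SpO2 values to PaO2 use the attached oxygen conversion tables". For screening, footnote v of the Appendix A schedule has oxygenation evaluated "either directly by arterial blood gas test or by calculation of PaO₂ from SpO₂, in case it is not possible" to draw arterial blood. The synopsis has equivalent screening text, so it contains both rules.

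**Cut-offs.** Appendix C and SAP Appendix 5 both grade the lung on PaO2/FiO2. No SpO2/FiO2 cut-offs appear anywhere. SAP Appendix 5 has no SpO2 rule, SpO2 table or FiO2 table. SAP section 1 says the SAP prevails where the documents differ, and refers the reader to the protocol for further definitions.

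**Who scores.** Under Protocol 6.2.8 site staff calculate the screening mSOFA; "otherwise all other clinical scores will be calculated retrospectively by the blinded statisticians". The visit sections, including Day 14 (4.3.7), allow SpO2 whenever a blood gas is not clinically indicated.

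**The concern.** The mSOFA total enters the trial at four places:

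- eligibility: screening total at least 3, with one organ at 2 or more;
- the randomization stratum: 3-4 versus above 4;
- the Day 14 component of NICCE: total of 1 or less;
- the reduction component of NICCE: a fall of at least 3 from baseline.

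A shift of 1 or 2 points in one organ can change any of them. Because only PaO2/FiO2 cut-offs exist, a scorer who follows 6.2.8.1 as written puts SpO2/FiO2 into cut-offs meant for another quantity, while a scorer who follows Appendix C does not. The same recorded reading can then be a NICCE success or a failure. If the rule is still open at unblinding, choosing it becomes a post hoc choice of primary endpoint.

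**Working it through.** The documents give no figure for this point, so there is none to reproduce.

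**Inputs**
- Cut-offs (Protocol Appendix C): above 400 scores 0, 400 or less scores 1, 300 or less scores 2. Scores 3 and 4 require respiratory support ("≤200 with respiratory support" for a score of 3). The grid below assumes no support, so it is capped at 2.
- SpO2 to PaO2 (Appendix C): 90→60, 91→62, 92→65, 93→69, 94→73, 95→79, 96→86, 97→96, 98→112, 99→145.
- FiO2 for nasal cannula (Appendix C): 0.24, 0.27, 0.30, 0.33, 0.36, 0.40.
- FiO2 on room air: 0.21. This is an assumption; Appendix C has no room-air row.

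**Formulas**
- Direct ratio: SpO2 / FiO2.
- Conversion: table PaO2 / FiO2.

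**Examples**

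| SpO2 | FiO2 | Direct ratio (score) | Conversion (score) |
|---|---|---|---|
| 90% | 0.21 | 90/0.21 = 428.6 (0) | 60/0.21 = 285.7 (2) |
| 91% | 0.21 | 91/0.21 = 433.3 (0) | 62/0.21 = 295.2 (2) |
| 92% | 0.21 | 92/0.21 = 438.1 (0) | 65/0.21 = 309.5 (1) |
| 95% | 0.21 | 95/0.21 = 452.4 (0) | 79/0.21 = 376.2 (1) |
| 96% | 0.21 | 96/0.21 = 457.1 (0) | 86/0.21 = 409.5 (0) |
| 99% | 0.33 | 99/0.33 = 300.0 (2) | 145/0.33 = 439.4 (0) |
| 99% | 0.36 | 99/0.36 = 275.0 (2) | 145/0.36 = 402.8 (0) |

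**Grid, 10 SpO2 values by 7 FiO2 values**

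| FiO2 | 0.21 | 0.24 | 0.27 | 0.30 | 0.33 | 0.36 | 0.40 | Total |
|---|---|---|---|---|---|---|---|---|
| Cells that differ, of 10 | 6 | 5 | 8 | 7 | 2 | 2 | 1 | 31 of 70 |

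The direct ratio scores lower in 23 cells and higher in 8. The gap is 2 points in 4 cells (room air at 90% and 91%; 99% at FiO2 0.33 and 0.36) and 1 point in the other 27. Without the assumed room-air row, 31 - 6 = 25 of 60 cells differ.

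SAP Appendix 5 uses strict inequalities and, for a score of 3, "< 200 and mechanically ventilated". With those cut-offs 32 of 70 cells differ (24 lower, 8 higher by direct ratio). At SpO2 99% and FiO2 0.33 the direct ratio is exactly 300, so the SAP gives 1 versus 0 there; the FiO2 0.36 example is unchanged. Across the whole Appendix C SpO2 range (80-99%), with or without support, no cell differs by more than 2 points.

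**What can change**
- *Day 14 component.* Room air, SpO2 91%, other organs 0: mSOFA is 0 (met) or 2 (not met).
- *Eligibility.* Room air, SpO2 90%, one other point: total 0 + 1 = 1 (not eligible) or 2 + 1 = 3 with one organ at 2 (eligible).
- *Stratum.* Room air, SpO2 90%, other organs totalling 3 with one at 2: total 3 (stratum 3-4) or 5 (stratum above 4).
- *Reduction.* Baseline 3 by conversion; Day 14 on room air at SpO2 94%, other organs 0. By conversion the fall is 3 - 1 = 2 (not met). If Day 14 were scored by direct ratio, it would be 3 - 0 = 3 (met).

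**The case against.** The best reply is that the documents lean to conversion. The Appendix C footnote sits on the mSOFA table itself and is not limited to one visit; the synopsis and Appendix A use conversion for screening. The schedule also asks sites to confirm readings of 95% or below, which is where conversion starts to score on room air (376.2 at 95%, 409.5 at 96%). Every cut-off is in PaO2/FiO2, and Appendix C is the only place that turns an SpO2 into a PaO2. The sentence in 6.2.8.1 is permissive and could be a loose pointer to that table. This shows which method was probably meant. It does not remove the conflict: the sentence appears three times, names a different quantity, and cites no table.

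Several stronger readings are tempting but not supported:

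- *Screening and Day 14 are scored by different rules.* Different people score them, so this is possible, but no text assigns a rule to either.
- *44% of patients are affected.* 31 of 70 counts grid cells with equal weight. On room air, 96-99% agrees throughout.
- *Most Day 14 lung scores rest on SpO2.* Neither document gives the share of patients without a blood gas.
- *SpO2 of 100% falls off the table and is set to 0 as missing.* The zero rule in SAP 5.2 is for an organ system that was not evaluated, and a recorded 100% is an evaluation. Using the 99% row, FiO2 up to 0.36 scores 0 anyway (145/0.36 = 402.8). The handling is unspecified, but no error follows from the text.
- *The treatment comparison is biased.* Later scores are calculated by blinded statisticians and site staff are blinded, so nothing here favours one arm.

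**Conclusion.** The point holds as a contradiction inside the primary endpoint, and the SAP's precedence over the protocol does not settle it because the SAP has no SpO2 rule. The two methods differ by up to 2 points. The room-air examples rest on an assumed FiO2 of 0.21; the 2-versus-0 result at SpO2 99% and FiO2 0.36 uses Appendix C values only.

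The consequence is misclassification and a NICCE definition that gives two answers for some readings. The number of patients affected, and any loss of power, cannot be computed without the SpO2 and FiO2 distributions and the share of visits without a blood gas. Which method is clinically preferable is not judged here.

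**What to change.** Before unblinding:

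1. Reconcile the passages to a single SpO2 rule for all visits. Appendix C, the synopsis screening text and Appendix A point to the conversion table. Align the sentences in the synopsis, 6.2.8.1 and Appendix E with the rule chosen.
2. Put that rule and the SpO2 and FiO2 tables into SAP Appendix 5. State how room air and an SpO2 above the 99% row are handled.
3. For the NICCE reduction component, score baseline and Day 14 by the same rule.
4. Report NICCE with the site-recorded screening score as a sensitivity analysis. Leave eligibility and stratum as randomized.

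The cost is wording plus one lookup in the scoring program; SpO2 and FiO2 are already recorded. The downside to disclose is that some recorded screening scores may change. For example, SpO2 99% at FiO2 0.36 plus one other point is 2 + 1 = 3 by direct ratio but 0 + 1 = 1 by conversion. A baseline rescored below 3 makes a 3-point fall unattainable, which is why step 4 is needed.
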